**duration of PFS (days) = date of progression or death due to any case – randomization date + 1;**

for those who are censored,

**duration of PFS (days) = date of censoring – randomization date + 1, with censor indicator indicating a censor.**

### **7.2.5 PFS: Primary Analysis**

The primary analysis of PFS will be performed using the ITT population and based on the data from the study.

Hypothesis testing between the two treatment arms will be performed using a log-rank test with an overall two-sided 0.05 level of significance via a model including treatment effects.

For each treatment arm the median duration of PFS and the proportion of patients alive and progression-free at six and 12 months will be estimated using the Kaplan-Meier method. For each estimate, a 95 % confidence interval will be reported. The hazard ratio and its 95 % confidence interval will also be reported.

### **7.2.6 PFS: Supportive and Sensitivity Analysis**

As a supportive analysis, PFS will be analyzed based on the modified ITT and PP populations. The same Cox models as defined for OS (see Section 7.1.3) will be made. In

addition, PFS will be analyzed in the subset of patients from MITT that have CR, PR or SD as best overall response.

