7.1 Efficacy (RECIST)

Response and progression will be evaluated using the international criteria proposed by the revised Response Evaluation Criteria in Solid Tumors (RECIST) guideline (version 1.1) [6]. Changes in the largest diameter (unidimensional measurement) of the tumor lesions and the shortest diameter in the case of malignant lymph nodes are used in the RECIST criteria.

During ongoing treatment, patients should be re-evaluated for response every 3 cycles (i.e. every 9 weeks).

The following text is a summary of RECIST 1.1.

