7.1.5.3 Evaluation of Best Overall Response

The best overall response is the best response recorded from the start of the treatment until disease progression/recurrence (taking as reference for progressive disease the smallest measurements recorded since the treatment started). The patient's best response assignment will depend on the achievement of both measurement and confirmation criteria.

Table 1: Response for patients with measurable disease (i.e., target disease)

Target Lesions	Non-Target Lesions	New Lesions	Overall Response	Best Overall Response when Confirmation is Required*
CR	CR	No	CR	≥4 wks. Confirmation**
CR	Non-CR/Non-PD	No	PR	≥4 wks. Confirmation**
CR	Not evaluated	No	PR	
PR	Non-CR/Non-PD/not evaluated	No	PR	
SD	Non-CR/Non-PD/not evaluated	No	SD	documented at least once ≥4 wks. from baseline**
PD	Any	Yes or No	PD	no prior SD, PR or CR
Any	PD***	Yes or No	PD	
Any	Any	Yes	PD	

* See RECIST 1.1 manuscript for further details on what is evidence of a new lesion.

** Only for non-randomized trials with response as primary endpoint.

*** In exceptional circumstances, unequivocal progression in non-target lesions may be accepted as disease progression.

Note: Patients with a global deterioration of health status requiring discontinuation of treatment without objective evidence of disease progression at that time should be reported as “*symptomatic deterioration*”. Every effort should be made to document the objective progression even after discontinuation of treatment.

Table 2: Tumor response for patients with non-measurable disease (i.e., non-target disease)

Non-Target Lesions	New Lesions	Overall Response
CR	No	CR
Non-CR/non-PD	No	Non-CR/non-PD*
Not all evaluated	No	not evaluated
Unequivocal PD	Yes or No	PD
Any	Yes	PD

* 'Non-CR/non-PD' is preferred over 'stable disease' for non-target disease since SD is increasingly used as an endpoint for assessment of efficacy in some trials so to assign this category when no lesions can be measured is not advised.

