### **3.2 Modified Intent-to-Treat Population**

A modified Intent-to-Treat (MITT) population will consist of all randomized patients, who received at least one dose of study treatment, i.e. the MITT population will exclude patients who never received study treatment.

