### **7.2.4 PFS: Definition**

PFS is defined as the number of days between randomization and the date of progression or death that occurred up to the end of study. PFS for patients who progress and then subsequently die will be the number of days between randomization and the date of progression is first observed.

Progression should be confirmed as specified. PFS data will be censored for subjects whose PFS status cannot be determined. The table below summarized rules of determining the dates of progression and censoring:

Situation	Date of Progression or Censoring	Outcome
No baseline tumor assessments	Randomization	Censored
Progression documented between scheduled visits	Date of the documented progression	Progressed
No progression	Date of last visit with adequate assessment	Censored
Treatment discontinuation for undocumented progression	Date of last visit with adequate assessment	Censored
Treatment discontinuation for toxicity or other reason	Date of last visit with adequate assessment	Censored
New anticancer treatment started	Date of last visit with adequate assessment	Censored
Death between adequate assessment visits	Date of death	Progressed
Death or progression after more than one missed visit	Date of last visit with adequate assessment	Censored

Once the dates of progression, survival, and censoring are derived, PFS will be calculated as follows:

For those who died or progressed up to the end of the study,

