### 7.4 Adjustments for Multiplicity

One non-binding efficacy interim analysis is planned for this study. Lan-DeMets implementation of the O'Brien-Fleming alpha-spending function will be used to control

the overall Type I error rate at 0.05. The study has one primary efficacy endpoint; no p-value adjustment for multiple endpoints is required.

Two key secondary efficacy variables, PFS and ORR will also be analyzed for potential labeling claims. Hierarchical testing procedures will be used to control the Type I Error at the 0.05 level. Specifically, the superiority of the active treatment will be tested at a two-sided significance level of 0.05 for OS first, then for PFS, and then for ORR. The superiority claim for an efficacy outcome can be made only if all previous claims are successfully made.

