## 12.5 Appendix E – List of Tables/Graphs and Listings

### List of Statistical Tables

Number	Description CODE: GREEN = topline; needed first
Table 14.1.1.1	Patient disposition
Table 14.1.1.2	Patient disposition by investigational site
Table 14.1.1.3	Patient disposition by territory
Table 14.1.2	Major protocol deviations
Table 14.1.3.1	Patients demographics and baseline characteristics (ITT)
Table 14.1.3.2	Patients demographics and baseline characteristics (safety)
Table 14.1.4.1	History of endometrial cancer (ITT)
Table 14.1.4.2	History of endometrial cancer (safety)
Table 14.1.5	Prior treatment for endometrial cancer
Table 14.1.6.1	Prior medications
Table 14.1.6.2	Concomitant medications
Table 14.1.7.1	Treatment exposure (ITT)
Table 14.1.7.2	Treatment exposure (safety)
Table 14.1.7.3	Treatment – mode of administration (ITT)
Table 14.1.8.1	Treatment modifications (ITT)
Table 14.1.8.2	Treatment modifications (safety)
Table 14.1.9	Post-study treatment anticancer therapy
Table 14.2.1	Overall survival: primary analysis (ITT)
Table 14.2.2	Overall survival: sensitivity analysis 1 (PP)
Table 14.2.3	Overall survival: sensitivity analysis 2 (MITT)

Table 14.2.4	Overall survival: sensitivity analysis 3 (ITT, censoring at time subject drops out due to AE)
Table 14.2.5.1	Overall survival: sensitivity analysis 4: part 1 (Cox models for treatment and each covariate separately)
Table 14.2.5.1	Overall survival: sensitivity analysis 4: part 2 (multivariate Cox model)
Table 14.2.6	Overall response rate: primary analysis
Table 14.2.7	Overall response rate: sensitivity analysis 1 (PP)
Table 14.2.8	Overall response rate: sensitivity analysis 2 (MITT)
Table 14.2.9.1	Overall response rate: sensitivity analysis 3: part 1 (logistic regression models for treatment and each covariate separately)
Table 14.2.9.2	Overall response rate: sensitivity analysis 3: part 2 (multivariate logistic regression model)
Table 14.2.10	Duration of overall response
Table 14.2.11	Duration of stable disease
Table 14.2.12	Duration of follow-up
Table 14.2.13	Progression-free survival: primary analysis
Table 14.2.14	Progression-free survival: sensitivity analysis 1 (PP)
Table 14.2.15	Progression-free survival: sensitivity analysis 2 (MITT)
Table 14.2.16	Progression-free survival: sensitivity analysis 3 (MITT – selection of patients with CR, PR or SD as best overall response)

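### PFS restricted to patients with CR, PR or SD as best response describes response-selected, non-randomised groups and is not a sensitivity analysis of the ITT PFS effect

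*SAP*

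**What the plan says.** SAP 7.2.6 first plans PFS in the MITT and PP populations, then adds that "PFS will be analyzed in the subset of patients from MITT that have CR, PR or SD as best overall response". Appendix E gives this its own table, 14.2.16, titled "Progression-free survival: sensitivity analysis 3 (MITT – selection of patients with CR, PR or SD as best overall response", and its own Kaplan-Meier plot, Figure 14.2.8. It is numbered alongside the PP and MITT analyses.

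Four other places define what this means:

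- MITT (SAP 3.2) is "all randomized patients, who received at least one dose of study treatment", so the subset narrows a near-complete population by outcome.
- Protocol 7.1.5.3: "The best overall response is the best response recorded from the start of the treatment until disease progression/recurrence".
- Protocol 7.1 schedules tumour assessment every three cycles, that is every 9 weeks, during treatment.
- SAP 7.2.4: "PFS is defined as the number of days between randomization and the date of progression or death that occurred up to the end of study". No different starting point is given for the subset.

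The main PFS analysis is separate. SAP 7.2.5 says "The primary analysis of PFS will be performed using the ITT population and based on the data from the study", and SAP 7.4 tests at a "two-sided significance level of 0.05 for OS first, then for PFS, and then for ORR". The subset is not a step in that hierarchy. Neither section 7.2.6 nor Appendix E adds a landmark, a caution on interpretation or a descriptive-only label. Protocol 9.5.1 does not contain the analysis; the SAP's document history lists it under version 4.

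**The concern.** Membership is decided after randomisation by something that is partly the endpoint itself. A patient who progresses or dies before a CR, PR or SD can be recorded has an early PFS event and is excluded because of it. Two things follow. Every member carries event-free time back to randomisation, so medians rise in both arms. And if treatment changes who gets past the first assessment, the patients left in the two arms need not be alike. The plan itself expects such an effect: ORR, built on the same best overall response, is a tested key secondary endpoint.

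A sensitivity analysis keeps the question and varies an assumption. This analysis changes the population and gives up the randomised comparison. PFS is meant for possible labelling claims (SAP 7.4) in an open-label trial. A table under this label could be quoted as evidence that the PFS result is robust, or used against a real effect, and would support neither.

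**Working it through.** **Plan's own figures.** None exist for PFS. The only sizing is for OS: hazard ratio 9/12 = 0.75, and 4 × (1.960 + 0.842)² / (ln 0.75)² gives 380 deaths (Schoenfeld; 385 by Freedman) against 384 stated. That reproduces but does not enter this point.

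**Inputs.** From the documents: 9-week scan interval, PFS from randomisation, about 250 patients per arm. Phase II (Protocol 1.2.2) had CR + PR + SD of 69.8% per reviewer and 76.7% per investigator, so roughly 23–30% fell outside; this is only an indication of subset size. Assumed: control median PFS 4 months; gamma-distributed patient heterogeneity with variance v = 0, 0.5 or 1; within-patient hazard ratio r = 0.75 or 0.60; subset approximated by PFS beyond s = 9 weeks = 63/30.44 = 2.07 months.

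**Step 1, medians.** For v > 0, control survival is S(t) = (1 + vLt)^(−1/v) with L = (2^v − 1)/(4v). The subset median solves S(t) = ½S(s), so t = [2^v(1 + vLs) − 1]/(vL).

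- v = 0 (exponential): 2.07 + 4 = 6.1 months
- v = 0.5: L = 0.2071, 1 + vLs = 1.214, t = (1.414 × 1.214 − 1)/0.1036 = 6.9 months
- v = 1: L = 0.25, 1 + vLs = 1.5175, t = (2 × 1.5175 − 1)/0.25 = 8.1 months

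A 4-month median therefore becomes about 6 to 8 months through selection alone.

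**Step 2, constant r.** The observed hazard ratio at time t is r(1 + vLt)/(1 + rvLt). With v = 0 it is r throughout, so the subset hazard ratio is unchanged. With v = 1 and r = 0.75 it is 0.75 at the start and 0.75 × 1.5175/1.388 = 0.82 at week 9, then drifts towards 1. The subset discards the early events, where the ratio is strongest, and keeps the attenuated part.

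**Step 3, effect only in the first 9 weeks.** After week 9 the observed ratio is (1 + vLt)/(1 + vLt − v(1 − r)Ls). With v = 0 it is exactly 1. With v > 0 it exceeds 1. At week 9:

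- v = 0.5: 1.214/(1.214 − 0.054) = 1.05 for r = 0.75, and 1.214/(1.214 − 0.086) = 1.08 for r = 0.60
- v = 1: 1.5175/(1.5175 − 0.129) = 1.09 for r = 0.75, and 1.5175/(1.5175 − 0.207) = 1.16 for r = 0.60

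It then declines towards 1.

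**Step 4, Cox hazard ratios averaged over follow-up.**

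| Assumed structure | All patients | Subset |
|---|---|---|
| Homogeneous, constant 0.75 | 0.75 | 0.75 |
| Homogeneous, effect in first 9 weeks only | below 1 | 1.00 |
| Heterogeneous (v 0.5–1), constant 0.75 | about 0.82–0.87 | about 0.84–0.91 |
| Heterogeneous (v 0.5–1), first 9 weeks only, 0.75 or 0.60 | about 0.91–0.96 | about 1.03–1.09 |
| Mixture: 10–25% moved by AEZS-108 from early progression to short-lived SD | 0.78–0.94 | 1.08–1.38 |
| Mixture: early progression caused by AEZS-108 in 20% | 1.15 | 0.79 |

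The heterogeneous rows move by a few hundredths with the follow-up cut; cutting at 24 months gives 0.81–0.84 to 0.83–0.88 for the third row. In one case of the fifth row, 50% are stable on either drug, 20% are stabilised only by AEZS-108 (median 2 months after week 9) and 30% progress early on either. The all-patient hazard ratio of 0.85 then becomes 1.22 in the subset.

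**Step 5, size against noise.** About 500 × 0.70 = 350 subset events, if all are observed, give a standard error of log hazard ratio of 2/√350 = 0.107. ln 1.03 = 0.030 and ln 1.09 = 0.086, so the sign change in the fourth row is 0.3 to 0.8 standard errors.

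**Step 6, landmark.** Under the approximation nobody in the subset has an event before week 9. The risk sets at each event are the same whether time runs from randomisation or from week 9, so the Cox hazard ratio is identical. A landmark changes the time axis, not the selection.

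**The case against.** Several points on the other side stand.

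- The SAP says PFS will be analysed in the subset. It does not state a log-rank test or hazard ratio there; those are specified for the ITT analysis in 7.2.5. A between-arm comparison is inferred from the sensitivity-analysis label and the company of the PP and MITT tables. It is the natural reading, but an inference.
- No decision rests on it. Primary PFS is ITT and the hierarchy runs OS, PFS, ORR. The table title also discloses the selection.
- Distortion of the hazard ratio is not automatic. It needs patient heterogeneity or a treatment effect concentrated in particular patients. With heterogeneity and a constant effect, the shift is a modest attenuation.
- The guaranteed event-free time does not itself bias the comparison between arms (Step 6).
- The calculated subset is a proxy. Earlier reassessment is allowed, and Protocol 7.1.5.3 scores non-progressing non-measurable disease as Non-CR/non-PD rather than SD. The SAP does not say whether such patients belong.

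A reader might infer that this analysis will reverse the treatment effect. The documents do not support that: they contain no PFS inputs, and the large reversals in Step 4 come from assumed patient mixtures. What the objection leaves untouched is the label. However small the shift, a response-selected comparison says nothing about the robustness of the ITT result.

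**Conclusion.** The point holds as a matter of labelling and interpretation, and is minor. The subset is defined by a post-randomisation outcome that overlaps with PFS, so its arms are not randomised groups and the output is not a sensitivity analysis of the ITT effect. That follows from the text and needs no assumption.

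The sizes do rest on assumptions: control median 4 months, gamma heterogeneity, membership approximated by PFS beyond 9 weeks. On these, medians rise from 4 to about 6–8 months. The hazard ratio is unchanged with homogeneous patients and proportional hazards, moves from about 0.82–0.87 to 0.84–0.91 with heterogeneity, and crosses 1 slightly (about 0.91–0.96 to 1.03–1.09) when heterogeneity is combined with an effect limited to the first 9 weeks. Larger distortion, in either direction, needs stronger assumptions.

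It would also be wrong to infer that the PFS claim or type I error is compromised. The subset lies outside the testing hierarchy, and primary PFS uses all randomised patients.

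**What to change.** Remove this analysis from the PFS sensitivity analyses in SAP 7.2.6 and Appendix E. Alternatively, keep Table 14.2.16 and Figure 14.2.8 as Kaplan-Meier summaries by arm, with no log-rank test and no hazard ratio, retitled as descriptive results in a non-randomised, response-selected subset. If kept, state whether patients with Non-CR/non-PD as best response are included.

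Starting the curves at week 9 is optional. It removes the guaranteed event-free time but leaves the selection, so it cannot replace the relabelling or the removal of the test and hazard ratio.

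The change is to SAP wording and table and figure titles only. The downside is the loss of one supportive comparison. Little descriptive information goes with it, because SAP 7.2.3 already plans duration of response and duration of stable disease.

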### 7.2.7 Quality of Life

Change from baseline in Quality of life will be analyzed via mixed model analysis with treatment effect, visit, its interaction, baseline quality of life score and its interaction with visit as covariates. The treatment effect and treatment difference will be estimated and the 95 % confidence interval of the estimates will be presented.

#### 7.2.7.1 QoL Scoring

The following sections describe the scoring algorithms used for both the QLQ-C30 and QLQ-EN24 questionnaires. Scoring procedures are similar for both questionnaires and can be found in the EORTC QLQ-C30 Scoring Manual, version 3.0 (Fayers et al. 2001) and the EN24 summary document. All scales and the single-item measures range from 0 to 100.

##### 7.2.7.1.1 QLQ-C30

For all scales, calculate the raw score (RS) of a scale using the mean of the item scores in the scale as follows:  $RS = (S_1 + S_2 + \dots + S_n) / n$

where  $S_i$ :  $i=1, \dots, n$  are the item scores and  $n$  is the number of items with valid scores, assuming the number of items with valid scores meets the minimum requirement as specified in Table 1 or this score will be assumed missing.

Use a linear transformation to standardize the raw score in order that scores will range from 0-100:

$$\text{Global Health Status/QOL} = \{(RS-1)/\text{range}\} * 100$$

$$\text{Functional Scales} = \{1 - ((RS-1)/\text{range})\} * 100$$

$$\text{Symptom Scales} = \{(RS-1)/\text{range}\} * 100$$

where range for each scale is defined in Table 1.

**Table 1: QLQ-C30 scales and scoring details**

	Number of Items	Item Range a	Item Numbers	Minimum Not Missing
Global Health Status/QOL	2	6	29,30	1
Functional Scales				
Physical Functioning	5	3	1-5	3
Role Functioning	2	3	6,7	1
Emotional Functioning	4	3	21-24	2
Cognitive Functioning	2	3	20,25	1
Social Functioning	2	3	26,27	1
Symptom Scales / Items				
Fatigue	3	3	10,12,18	2
Nausea / Vomiting	2	3	14,15	1

	Number of Items	Item Range a	Item Numbers	Minimum Not Missing
Pain	2	3	9,19	1
Dyspnoea	1	3	8	N/A
Insomnia	1	3	11	N/A
Appetite Loss	1	3	13	N/A
Constipation	1	3	16	N/A
Diarrhoea	1	3	17	N/A
Financial Difficulties	1	3	28	N/A

a Range is the difference between the maximum possible value of the raw score and the minimum possible value.

QLQ-C30 scale scores range from 0 to 100 with higher scores representing a better health state for the functional scales and lower scores representing a better health state for symptom scores.

#### 7.2.7.1.2 QLQ-EN24

For all scales, calculate the raw score (RS) of a scale using the mean of the item scores in the scale as follows:

$$RS = (S_1 + S_2 + \dots + S_n) / n$$

where  $S_i$ :  $i=1, \dots, n$  are the item scores and  $n$  is the number of items with valid scores, assuming the number of items with valid scores meets the minimum requirement as specified in Table 2 or this score will be assumed missing.

Use a linear transformation to standardize the raw score in order that scores will range from 0-100:

$$\text{Functional Scales} = \{1 - (RS-1)/\text{range}\} * 100$$

$$\text{Symptom Scales} = \{(RS-1)/\text{range}\} * 100$$

where range for each scale is defined in Table 2.

**Table 2: QLQ-EN24 scales and scoring details**

	Number of Items	Item Range a	Item Numbers	Minimum Not Missing
Functional Scales				
Sexual Interest	1	3	49	N/A
Sexual Activity	1	3	50	N/A
Sexual Enjoyment	1	3	54	N/A
Symptom Scales / Items				
Lymphoedema	2	3	31-32	1
Urological symptoms	4	3	34-37	2

	Number of Items	Item Range a	Item Numbers	Minimum Not Missing
Gastrointestinal symptoms	5	3	38-42	3
Poor body image	2	3	47-48	1
Sexual/vaginal problems	3	3	51-53	2
Pain in back and pelvis	1	3	33	N/A
Tingling/numbness	1	3	43	N/A
Muscular pain	1	3	44	N/A
Hair loss	1	3	45	N/A
Taste change	1	3	46	N/A

a Range is the difference between the maximum possible value of the raw score and the minimum possible value.

A high score for the functional scales represents a high level of functioning, while a high score for the symptom scales represents a high level of symptoms or problems. Symptoms related to sexual/vaginal problems (including items 51-53) are optional.

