40. Have you been troubled by passing wind?	1	2	3	4
41. Have you had cramps in your abdomen?	1	2	3	4
42. Have you had a bloated feeling in your abdomen?	1	2	3	4
43. Have you had tingling or numbness in your hands or feet?	1	2	3	4
44. Have you had aches or pains in your muscles or joints?	1	2	3	4
45. Have you lost hair?	1	2	3	4
46. Has food and drink tasted differently from usual?	1	2	3	4

Please go on to the next page

ENGLISH

During the past week:		Not at all	A little	Quite a bit	Very much
47.	Have you felt physically less attractive as a result of your disease or treatment?	1	2	3	4
48.	Have you felt less feminine as a result of your disease or treatment?	1	2	3	4
 During the past 4 weeks:					
		Not at all	A little	Quite a bit	Very much
49.	To what extent were you interested in sex?	1	2	3	4
50.	To what extent were you sexually active?	1	2	3	4
Answer these questions only if you have been sexually active during the past 4 weeks:					
51.	Has your vagina felt dry during sexual activity?	1	2	3	4
52.	Has your vagina felt short and / or tight?	1	2	3	4
53.	Have you had pain during sexual intercourse or other sexual activity?	1	2	3	4
54.	Was sexual activity enjoyable for you?	1	2	3	4

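### The SAP's QLQ-EN24 formula reverses three positively worded items, so sexual interest, activity and enjoyment are scored with the wrong sign

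*SAP*

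**What the plan says.** SAP 7.2.7.1.2 gives two transformations for the QLQ-EN24. Functional scales use {1 − (RS − 1)/range} × 100, which reverses the raw score. Symptom scales use {(RS − 1)/range} × 100, which does not.

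SAP Table 2 assigns three scales to the functional group, each a single item with range 3: Sexual Interest (item 49), Sexual Activity (item 50) and Sexual Enjoyment (item 54). The remaining ten scales are symptom scales. The note under the table fixes the direction: "A high score for the functional scales represents a high level of functioning".

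Protocol Appendix 6 prints the items. Item 49 asks "To what extent were you interested in sex", item 50 asks in the same form about being sexually active, and item 54 asks "Was sexual activity enjoyable for you". Answers are coded 1 = *Not at all*, 2 = *A little*, 3 = *Quite a bit*, 4 = *Very much*.

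SAP 7.2.7.2.3 compares changes from baseline in the EN24 scores between arms with a mixed model for repeated measures. SAP 7.2.7.2.1 extends to the EN24 the alternative hypothesis that quality of life is better on AEZS-108.

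**The concern.** Reversal is needed when a high raw answer means poor functioning. Items 49, 50 and 54 are worded the other way, so reversing them gives the top score to a patient with no interest, activity or enjoyment. That contradicts the direction stated under Table 2. Nothing in the SAP recodes these items before scoring or exempts them from the functional formula.

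Patient-reported quality of life is a secondary objective of the trial, and the EN24 result is read by its sign. A reader relying on the note under Table 2 would take a loss of function on AEZS-108 relative to doxorubicin for a gain, or the reverse. The scored output would not reveal the error: scores stay within 0 to 100, and the tests give the same two-sided p-values.

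**Working it through.** **Inputs**
- Functional and symptom formulas: SAP 7.2.7.1.2.
- Functional items 49, 50 and 54, one item each, range 3: SAP Table 2. With one item, RS is the answer itself.
- Stated direction (high = high functioning): note under SAP Table 2.
- Item wording and answer codes 1 to 4: Protocol Appendix 6.

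**Step 1. Evaluate the formula.** Let F = {1 − (RS − 1)/3} × 100 be the SAP score and D = {(RS − 1)/3} × 100 the unreversed score.

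| Answer | RS | F (SAP as written) | D (unreversed) |
|---|---|---|---|
| Not at all | 1 | 100 | 0 |
| A little | 2 | 66.7 | 33.3 |
| Quite a bit | 3 | 33.3 | 66.7 |
| Very much | 4 | 0 | 100 |

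The SAP's stated 0–100 range is reproduced by F. Its stated direction is not; only D gives it.

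**Step 2. Effect on change scores.** At every level F = 100 − D. So for any patient

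F(visit) − F(baseline) = −[D(visit) − D(baseline)].

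Example: a fall in interest from 3 to 2 gives 66.7 − 33.3 = +33.3 under the SAP formula, and 33.3 − 66.7 = −33.3 unreversed.

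**Step 3. Effect on the model.** The mixed model has change from baseline as outcome, with treatment, visit, their interaction, baseline, and baseline by visit. Replacing D by 100 − D changes the sign of the outcome and replaces baseline by 100 − baseline. The constant 100 is absorbed by the visit terms. Least-squares mean changes and treatment differences therefore change sign exactly, and their standard errors and two-sided p-values stay the same. As a simpler numerical check of the sign change, a two-sample t-test on simulated change scores (100 patients per arm, purely illustrative) gave a difference of −22.67 with F and +22.67 with D, and the same two-sided p-value.

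**Step 4. Is the same reversal wrong elsewhere?** No. The QLQ-C30 functional items visible in Protocol Appendix 6 (items 1 to 7) ask about trouble, needing help or rest, or being limited. There RS = 1 is the best state, and the reversal correctly gives it 100. The EN24 symptom items are scored without reversal, so a high score means more symptoms, as the SAP says.

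**Extent.** Table 2 has 3 functional and 10 symptom scales. The error touches 3 of 13 EN24 scales, which are all of its functional scales.

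**The case against.** The contradiction itself is not in dispute. The case on the other side is about how much it matters.

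- *Not confirmatory.* SAP 7.4 limits formal testing to OS, then PFS, then ORR. The quality-of-life hypothesis is written first for the QLQ-C30 global scale, which is unaffected. This stands: no confirmatory claim changes.
- *Recoverable.* The faulty score is 100 minus the right one, so effect size and two-sided p-values survive. This stands, but direction is what a quality-of-life result is read for.
- *Detectable.* SAP Appendix E plans raw and change summaries of individual EN24 questions (Tables 14.2.18.4 and 14.2.19.4) and a listing of individual answers. For single-item scales these show the unreversed direction. This helps an alert reader, but it does not correct the score tables (14.2.18.2 and 14.2.19.2) or the mixed-model table (14.2.20.2). The report would instead contradict itself.
- *Another source.* SAP 7.2.7.1 also refers to an EN24 summary document, which was not available for this check. A programmer following it might score the items differently. This makes the wrong sign conditional on programming the formula as printed. It does not excuse the formula: if that document gives another rule, the SAP conflicts with its own source.
- *Size.* The 33.3 points per category is a property of the scale and not an expected bias. Patients already at 4 cannot move up, and item 54 is answered only by patients sexually active in the past 4 weeks. This stands.

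**Conclusion.** The concern holds. For items 49, 50 and 54 the formula in SAP 7.2.7.1.2 and the interpretation under Table 2 cannot both be right. If the formula is followed, each one-category change is reported as 33.3 points in the wrong direction, and every summary of change and every treatment difference on these three scales has the opposite sign to its stated meaning.

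The conclusion rests on the item wording and codes printed in Protocol Appendix 6, on the SAP's own statement of direction, and on the formula being programmed as printed. It does not touch the other ten EN24 scales, the QLQ-C30, two-sided p-values, or the OS, PFS and ORR analyses. It should still be corrected, because a rule that yields a wrong-signed estimate when followed is an error and not a choice of method.

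**What to change.** In SAP 7.2.7.1.2, score items 49, 50 and 54 as {(RS − 1)/range} × 100, and state that these positively worded items are not reversed. Keep the sentence under Table 2, which then agrees with the scores: *Very much* gives 100 and *Not at all* gives 0. Leave the EN24 symptom formula and all QLQ-C30 formulas as they are. Confirm the rule against the EN24 summary document cited in SAP 7.2.7.1, and check in the program that each of the three scores rises with the corresponding raw answer.

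The alternative is to keep the formula and rewrite the interpretation. That is less good, because functional scales would then run in opposite directions in the two questionnaires.

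The cost is one formula in the SAP and the matching program line, with no new data. It should be done before database lock, by which time the SAP must be final. If lock has passed, SAP 4.6 requires the change to be documented in the clinical study report.
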